**1. PROTOCOL SYNOPSIS**

Title of Study:	Clinical Evaluation of the Sebum Reduction Induced by Clascoterone Cream 1%
Study Period:	52 weeks (Baseline, Week 2, Week 4, Week 6, Week 8, Week 10, Week 12, Week 16, Week 20, Week 24, Week 28, Week 32, Week 36, Week 40, Week 44, Week 48, Week 52)
Test Products	Winlevi (Clascoterone Cream 1.0%) Applied to entire face morning and evening.
Objective:	
The objectives of this research are as follows:
 
 
1. The primary objective is to assess the ability of clascoterone cream 1% to reduce casual facial sebum at weeks 4, 8, 12, 16, 20, 24, 28, 32, 36, 40, 44, 48, and 52.
 
2. The secondary objective is to assess the ability of clascoterone cream 1% to reduce casual facial sebum at weeks 2, 6, and 10.
 
3. The tertiary objective is to demonstrate microbiome changes after 8, 12, and 52 weeks of clascoterone 1.0% facial application.
 

Design:	
Female and male subjects will be enrolled in this single site study to evaluate the effect of clascoterone cream 1.0% on facial sebum production and acne. Subjects who sign consent and meet all inclusion criteria and none of the exclusion criteria will be enrolled at the baseline visit. Subjects will use their own approved skin care products unchanged for the duration of the study.
 
At baseline visit, subjects will receive the study product. The dermatologist investigator will assess facial appearance in terms of oily appearance, pore size, and facial shine. In addition, she will perform a global acne assessment (IGA), inflammatory lesion counts (papules, pustules) and non-inflammatory lesion counts (open comedones, closed comedones). The dermatologist investigator will assess the tolerability criteria of peeling, dryness, redness, and swelling on a 5-point ordinal scale (0=none, 1=minimal, 2=mild, 3=moderate, 4=severe). Three casual sebumeter measurements will be taken from the central forehead 2-4 hours after the subjects washed prior to presenting to the research center.
 
Subjects will assess the performance of their acne treatment regimen by completing a consumer self-assessment/treatment perception questionnaire provided by the sponsor and a tolerability assessment in terms of stinging, itching, and burning. All tolerability assessments will be made on a 5-point ordinal scale (0=none, 1=minimal, 2=mild, 3=moderate, 4=severe) at each visit. Subjects will be given their diaries and study products and asked to return to the research center in 2 weeks. A reminder text will be sent to

	
encourage compliance prior to the week 2 visit.
 
Subjects will return to the research center at Week 2, Week 4, Week 6, Week 8, Week 10, Week 12, Week 16, Week 20, Week 24, Week 28, Week 32, Week 36, Week 40, Week 44, Week 48, Week 52 for the same assessments. Old study product and diaries will be collected and new diaries and study product dispensed as needed. All the same assessments will be performed as at baseline for all visits. Subjects will continue participation for 52 weeks, at which time their study participation will be completed.
 
Microbiome swabbing for analysis by [REDACTED] will be obtained from all 40 subjects at baseline, week 8, week 12, and week 52.
 
(There is an allowance for an unscheduled visit at any time, if necessary.)

Study Population:	Healthy female and male subjects 12+ years of age Fitzpatrick skin types I-VI with mild to moderate acne (10-100 total non-inflammatory lesions (open comedones and closed comedones), 10-50 total inflammatory lesions, no cysts, and up to 2 nodules (if deemed appropriate by the PI) on the face.
Number of Subjects:	40 subjects
Inclusion Criteria:	
 
1. Males and females 12+ years of age.
 
2. Subjects with mild to moderate acne.
 
3. Subjects must possess 10-100 total non-inflammatory lesions (open comedones and closed comedones), 10-50 total inflammatory lesions, no cysts, and up to 2 nodules (if deemed appropriate by the PI) on the face.
 
4. Subjects with all Fitzpatrick skin types I-VI.
 
5. Subjects who agree to use only the study products for acne treatment. No other medicated cleansers or moisturizers or acne treatments of any kind are allowed.
 
6. Subjects agree not to introduce any new colored cosmetics or skin care products while participating in the study (lipsticks, eye shadows, facial foundations, blush, powder, cleansers, moisturizers).
 
7. Subjects agree to arrive at all visits with a clean face, having washed his/her face and removed all facial and eye makeup products within 2 hours to 4 hours prior to the visit and is not to use/apply any topical facial product(s) until the visit is completed.
 
8. No known medical conditions that, in the investigator's opinion, may interfere with study participation.
 
9. Women of childbearing potential must be willing to use a form of birth control during the study. For the purpose of this study, the following are considered acceptable methods of birth control: oral contraceptives, Norplant®, Depo-Provera®, double barrier methods (e.g., condom and spermicide) and abstinence.
 
10. Subjects are dependable and able to follow directions and willing to comply with the schedule of visits.
 

	
 
11. Subjects in generally good physical and mental health.
 
12. Able to read, write, speak, and understand English
 
13. Individual (and/or his/her legally acceptable representative, as applicable) has signed the Consent for Photograph Release and ICD (and/or Assent Document, as applicable) including Health Insurance Portability and Accountability Act (HIPAA) disclosure.
 
14. Subject must avoid sun exposure, or use sunscreen if sun exposure is unavoidable.
 
15. Subject must avoid professional or facial spa procedures during the study.
 

Exclusion Criteria:	
 
1. Any dermatological disorder, which in the investigator's opinion, may interfere with the accurate evaluation of the subject's skin characteristics, except for the study condition of acne.
 
2. Subjects who are not willing to use the assigned study product to their face as instructed.
 
3. Subjects who have acne nodules/cysts representative of severe acne.
 
4. Subjects who are currently using, planning to use during the study or has used any of the following in the specified time range (based on subject report): 
 
- 1 month prior to Visit 1: Prescription (oral or topically applied on the face) antibiotics, inhaled steroids (except those prescribed for allergies), or hormones (pre- or post-menopausal hormone-replacement therapy; insulin, etc.), or other medications that could make skin more sensitive or have an effect on the skin, as determined by the PI or designee. Oral contraceptives are acceptable.
 
- 1 month prior to Visit 1: Prescription medication for acne (e.g. doxycycline, minocycline, clindamycin, sulfamethoxazole and trimethoprim [Bactrim], tetracycline, erythromycin, azithromycin, or Vibramycin®)
 
- 1 month prior to Visit 1: Topical prescription retinoids (e.g. Retin-A®, Retin-A Micro®, Renova®, Adapalene, Tazarotene, Avita®, Tazorac®, Avage®, Differin®), azelaic acid, benzoyl peroxide, dapsone, sodium sulfacetamide, Epiduo®, or other similar prescription drug on the face
 
- 6 months prior to Visit 1: Accutane or other oral retinoid
 
- 2 weeks prior to Visit 1: Any of the following on the face: 
 
• Light therapy
 
• OTC topical medications/products (including antiacne or antibacterial agents, topical anti-inflammatories, topical retinoids, etc.). Sunscreens (SPF) are acceptable.
 
 
 
 
 
5. Females who are pregnant, lactating, or planning to become pregnant
 

	
during the study or within 30 days of study completion. (Subject must document her response in either the source documentation or informed consent/assent forms).
 
 
6. Subject has a surgery and/or invasive medical procedure planned during the study.
 
7. Subject has observable suntan, scars, nevi, tattoo, excessive hair (including beard, mustache, or goatee), or other dermal conditions on the face that that could interfere with study evaluations or confound study results, as determined by the PI or designee.
 
8. Subject is taking medications that would mask an adverse event (AE) or influence the study results, including: 
 
- Immunosuppressive drugs and steroidal and/or non-steroidal anti-inflammatory drugs within 3 months before Visit 1 and during the study.
 
- Regular use of antihistamines within 1 month before Visit 1 and during the study.
 
 
 
9. Subject has a history of or a concurrent health condition/situation, which in the opinion of the PI, if medically qualified, or Study Physician, may put the individual at significant risk, confound the study results, or interfere significantly with the individual's participation in the study.
 
10. Subject is an employee/contractor or immediate family member of the PI, Study Site, or Sponsor.
 
11. Subjects with clinically significant unstable medical disorders.
 
12. Subjects who are unwilling or unable to comply with the requirements of the protocol.
 
13. Subjects with any known allergies or sensitivities to the study acne products.
 
14. Subjects who are currently under the care of a dermatologist for acne.
 
15. Subjects who are currently experiencing an acne flare.
 
16. Subjects who have history of a psychological illness or condition that would interfere with their ability to understand and follow the requirements of the study.
 
17. Subjects having started hormone replacement therapies (HRT) or hormones for birth control less than 3 months prior to the study entry or who plan on starting, stopping or changing doses of HRT or hormones for birth control during the study.
 

Endpoints:	
Tolerability Endpoint: The tolerability endpoint is the investigator-assessed absence of skin irritation from the facial study acne products at any time during the study.
 
Safety Endpoint: The safety endpoint is the overall incidence of all adverse events reported during the study.

	
Primary Efficacy Endpoint: The primary efficacy endpoint is the reduction in causal sebum measurements from the forehead obtained with a sebumeter during the study.
 
Secondary Efficacy Endpoint: The secondary efficacy endpoint is the changes in the facial microbiome induced by 8, 12, and 52 weeks of clascoterone 1% cream application.
 
[REDACTED]
 
[REDACTED]

Measures:	
[REDACTED]
 
[REDACTED]
 
[REDACTED]
 
[REDACTED]
 
[REDACTED]
 
[REDACTED]
 
[REDACTED]
 
[REDACTED]
 
[REDACTED]
 
Sebumeter measurements: 3 sebumeter measurements will be taken from the forehead 2-4 hours after facial washing at each study visit.
 
Microbiome assessment: Swabbing of the cheek for microbiome analysis will be performed from all subjects at baseline, week 8, week 12, and week 52.

Statistical	Along with descriptive statistics (means, standard deviations and percentages),

Methods:	investigator and subject ordinal nonparametric data will be analyzed using the Wilcoxon signed rank test. Change will be considered significant at a p value less than or equal to 0.05. Numerical acne lesion counts (inflammatory, noninflammatory, and total lesions) and sebumeter measurements will be assessed with a Student's t test again with significance at a p value less than or equal to 0.05.
----------	---

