## **12. STATISTICAL METHODS**

Along with descriptive statistics (means, standard deviations and percentages), investigator and subject ordinal nonparametric data will be analyzed using the Wilcoxon signed rank test. Change will be considered significant at a p value less than or equal to 0.05. [REDACTED]

[REDACTED] sebumeter measurements will be assessed with a Student's t test again with significance at a p value less than or equal to 0.05.

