## **12.5 ENDPOINTS**

### **12.5.1 PRIMARY EFFICACY ENDPOINT**

The primary efficacy endpoint is the reduction in causal sebum measurements from the forehead obtained with a sebumeter during the study.

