### **12.5.2 SECONDARY EFFICACY ENDPOINT**

The secondary efficacy endpoint is the changes in the facial microbiome induced by 8, 12, and 52 weeks of clascoterone 1% cream application

[REDACTED]

[REDACTED]

[REDACTED]

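### No visit, testing order or success rule decides the primary sebum claim across 13 or 16 visits, so the stated 0.05 is not its error rate

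*Combined protocol and SAP*

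**What the plan says.** **Objectives (section 1, Protocol Synopsis).** The primary objective concerns the ability of the cream "to reduce casual facial sebum at weeks 4, 8, 12, 16, 20, 24, 28, 32, 36, 40, 44, 48, and 52": 13 visits, listed as equals. The next rank covers three earlier visits on the same measure: "The secondary objective is to assess the ability of clascoterone cream 1% to reduce casual facial sebum at weeks 2, 6, and 10". The third is "The tertiary objective is to demonstrate microbiome changes after 8, 12, and 52 weeks of clascoterone 1.0% facial application".

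**Endpoints (sections 12.5.1 and 12.5.2, with the same wording in sections 1 and 4).** "The primary efficacy endpoint is the reduction in causal sebum measurements from the forehead obtained with a sebumeter during the study". No visit is given. Section 8.1 and the sebumeter case report form schedule readings at every visit: baseline plus 16. Next comes "The secondary efficacy endpoint is the changes in the facial microbiome induced by 8, 12, and 52 weeks of clascoterone 1% cream application".

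**Test and level (sections 1, 12 and 12.2).** "sebumeter measurements will be assessed with a Student's t test again with significance at a p value less than or equal to 0.05". Section 12.2 makes the test two-sided.

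**Design (sections 10.6 and 12.1).** There is a single arm, and 40 subjects were chosen by the sponsor with no effect size, standard deviation or power given.

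The statistical methods paragraph in the synopsis can be read in full. It contains no multiplicity adjustment, testing order, summary across visits or success rule.

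**The concern.** The primary claim has no single definition. A significant result at any visit, at every visit, at the last visit or on average would each fit the text. The objective and the endpoint also disagree on which visits count: weeks 2, 6 and 10 are secondary in one and inside the primary in the other. Whoever reports the study could settle both questions after seeing the data.

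At stake is the meaning of the significance level. Demonstrating sebum reduction is the stated aim of the study. With one arm, no control group shows what chance alone produces. If several visits are tested at 0.05 and the favourable ones are reported, 0.05 no longer describes the risk of a false primary claim.

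The microbiome mismatch adds to the loose hierarchy. It is a labelling conflict and has no error rate of its own that could be computed.

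**Working it through.** **The plan's own figure.** The only stated error figure is 0.05 two-sided per test (section 12.2). That leaves 0.025 in the direction of a reduction. The plan gives no familywise rate to reproduce, and the sample size of 40 has no inputs from which to rebuild it.

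**Inputs from the documents.** k = 13 visits (primary objective) or k = 16 (primary endpoint); n = 40; two-sided 0.05; single arm, so the test is taken as change from baseline.

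**Assumptions, not in the documents.** One test per visit; success if any visit shows a significant reduction; no true change; no carried-forward values; a range of within-subject correlations.

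**Step 1: independent tests (upper reference).** Chance of at least one false reduction = 1 − (1 − 0.025)^k.
- k = 13: 1 − 0.975^13 = 28.0%
- k = 16: 1 − 0.975^16 = 33.3%

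**Step 2: why independence is unrealistic.** All changes share one baseline. If visits have equal variance σ² and equal correlation ρ, each change has variance 2σ²(1 − ρ), and two changes have covariance σ²(1 − ρ). Their correlation is therefore 0.5 whatever ρ is.

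**Step 3: simulation.** 20,000 trials per setting, n = 40, a t test on change from baseline at each visit. In the AR(1) rows, the correlation between two visits is r raised to the number of 4-week intervals between them. At a rate of 17%, the simulation standard error is √(0.17 × 0.83 / 20,000) ≈ 0.3 percentage points.

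| Correlation structure | False reduction, 13 visits | False reduction, 16 visits |
|---|---|---|
| Changes correlate 0.5 | 17.4% | 19.5% |
| AR(1), r = 0.3 | 16.6% | 18.7% |
| AR(1), r = 0.6 | 15.2% | 17.0% |
| AR(1), r = 0.8 | 13.6% | 15.3% |
| AR(1), r = 0.9 | 12.4% | 14.4% |
| Changes correlate 0.7 | 12.1% | 13.5% |
| Changes correlate 0.9 | 7.2% | 7.5% |

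The shared-baseline models (first five rows) give about 12-20%.

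**Step 4: the opposite rule.** If every visit had to show a significant reduction, the rate is 0.6% (13 visits) or 0.4% (16 visits) at correlation 0.9, and 0.8% for both at 0.95. It is lower still at smaller correlations.

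**Step 5: effect of the choice of remedy on power.** The standardised mean change detectable with 80% power at n = 40 (noncentral t) is 0.454 for one test at 0.05. For Bonferroni over 13 visits (0.05/13 = 0.00385) it is 0.624.

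**The case against.** The strongest reply is that the plan nowhere says each visit is tested separately or that one significant visit is enough. That is correct. Visit-by-visit testing is an inference from an objective written visit by visit, and the any-visit rule is one reading among several. Under an all-visits rule the plan would be conservative. What stands is that the text does not choose. The error rate runs from below 1% to about 20%, or more if visits were nearly independent, depending on an unwritten rule.

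A second reply is that the correlation is unknown, and that section 8.3 carries the last visit forward for subjects released for noncompliance, which would make later visits more alike. Both points are fair. They favour the lower part of the range, but even at a correlation of 0.9 the any-visit rate is nearly three times 2.5%.

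Three stronger readings should be resisted:
- A reader might infer that a false reduction claim is likely. No figure for a false reduction reaches 50%, even under independence.
- A reader might quote 1 − 0.95^13 = 49% or 1 − 0.95^16 = 56%. Those figures assume independence and count false increases, which would not support an endpoint defined as a reduction.
- A reader might say that weeks 2, 6 and 10 have no endpoint of their own. The contents list tertiary and quaternary efficacy endpoints (12.5.3 and 12.5.4) whose text is blacked out, so this cannot be judged.

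**Conclusion.** The concern holds as a missing definition. The plan offers 13 or 16 primary visits, one unadjusted two-sided 0.05 threshold, and no readable rule for turning the results into a primary conclusion. The stated 0.05 is therefore not the error rate of the primary claim.

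Under an any-visit rule, the false-reduction rate is about 12-20% against 2.5%. That rests on no true change, 40 subjects with complete data, a test at each visit and a shared baseline with the correlations shown. This is strong inflation, but well short of a probable false claim.

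The rank conflict for microbiome, third among objectives and second among endpoints, is plain on the page.

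**What to change.** Amend sections 1, 4, 12, 12.2 and 12.5.1 before any data review:

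1. Name one primary contrast: change from baseline in forehead sebum at a single stated visit, two-sided 0.05. Week 52 is one option. Any single visit named in advance controls the error equally well, and Week 52 is among the visits most exposed to the carry-forward rule in section 8.3.
2. Make the other 12 visits of the primary objective secondary. Test them with Holm, and only if the primary contrast is significant.
3. Report weeks 2, 6 and 10 as estimates with 95% confidence intervals.
4. Give microbiome the same rank in the synopsis objectives and in the endpoint sections (1, 4 and 12.5.2).

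**Cost.** Wording only; no added visits or subjects. Isolated significant visits could no longer be claimed as primary success. The secondary visits face a stricter threshold, with a first Holm step of 0.05/12 = 0.0042. The primary test itself keeps its detectable change of 0.454 standard deviations of the change at 80% power with 40 subjects, against 0.624 if Bonferroni were spread over 13 visits.

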### **12.2 SIGNIFICANCE LEVEL**

Significance is defined at the  $p < 0.05$  level based on a two-sided test.

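### An unadjusted 0.05 rule covers 14 non-sebum measures collected at 16 visits, with no visit for inference in the readable text: if every visit is tested, 224 tests and up to about 11 false positives if nothing changes

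*Combined protocol and SAP*

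**What the plan says.** The Statistical Methods entry in the synopsis (Section 1) sets one rule for two groups of data.

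- **Ordinal scales.** Section 12 states that "investigator and subject ordinal nonparametric data will be analyzed using the Wilcoxon signed rank test", and the synopsis says the same. The decision rule in both places is "Change will be considered significant at a p value less than or equal to 0.05".
- **Counts and sebum.** In the synopsis, "Numerical acne lesion counts (inflammatory, noninflammatory, and total lesions) and sebumeter measurements" go to a Student's t test, "again with significance at a p value less than or equal to 0.05". In Section 12 the part of this sentence before sebum is redacted.

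Section 12.2 adds that the threshold is a "level based on a two-sided test". It writes the threshold as strictly below 0.05, where the other two places allow equality. That small mismatch does not affect this point.

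The Design entry of the synopsis lists what is scored: "The dermatologist investigator will assess facial appearance in terms of oily appearance, pore size, and facial shine"; an IGA; "tolerability criteria of peeling, dryness, redness, and swelling on a 5-point ordinal scale"; and stinging, itching and burning scored by the subject. It has every baseline assessment repeated at each later visit, and the case report forms in Appendix I have a row for each visit.

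Individual visits are named for analysis only in the sebum objectives and, at weeks 8, 12 and 52, for the microbiome. The table of contents lists tertiary, quaternary and tolerability endpoints in Section 12.5, but the body text of those entries is redacted. The synopsis does show a tolerability endpoint: the investigator finding no skin irritation at any point in the study.

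**The concern.** The rule gives supporting measures the same licence to be called significant as the primary endpoint, without saying at which visit or in what order. With many scales and many visits, some changes will cross 0.05 by chance. The study has one arm, no code and 40 subjects, so no control group is available to expose a chance result. An isolated fall in pore size at one visit, or a rise in redness at another, could be reported as a product effect under the plan as written. Settling multiplicity for sebum alone would leave this rule in force for everything else.

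**Working it through.** The documents state no number of tests, family-wise error rate or power, so there is no figure of theirs to reproduce.

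**1. Measures** (synopsis Design and Statistical Methods; Appendix I forms)

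| Group | Measures | Number |
|---|---|---|
| Investigator, acne | IGA | 1 |
| Investigator, appearance | oiliness, pores, shine | 3 |
| Investigator, tolerability | peeling, dryness, redness, swelling | 4 |
| Subject, tolerability | stinging, itching, burning | 3 |
| Lesion counts | inflammatory, noninflammatory, total | 3 |
| **Total** | | **14** |

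**2. Visits.** Weeks 2, 4, 6, 8, 10, 12, then every 4 weeks from 16 to 52: 6 + 10 = 16 post-baseline visits.

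**3. Tests, if each measure is compared with baseline at each visit.** 14 × 16 = 224. Of these, the 7 tolerability scales account for 7 × 16 = 112 and the other 7 measures for 112.

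**4. Expected false positives.** Formula: tests × share of true nulls × 0.05.

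| Share of nulls true | Expected number |
|---|---|
| 100% | 224 × 0.05 = 11.2 |
| 75% | 8.4 |
| 50% | 5.6 |
| 25% | 2.8 |

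Under the complete null, half of the 11.2 (5.6) fall in each direction.

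**5. Correlation.** It leaves the mean alone but widens the spread. The check used 3,000 simulated null trials with n = 40, normal data and a baseline shared by all 16 visits.

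| Correlation between measures | Mean | Median | 5th–95th percentile | Trials with none |
|---|---|---|---|---|
| 0 | 11.1 | 10 | 4–22 | 0.1% |
| 0.3 | 11.3 | 9 | 3–26 | 0.4% |
| 0.6 | 11.0 | 7 | 1–36 | 2.8% |

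**6. Tests that do not run at exactly 5%.** These lower the figure.

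- *Sparse tolerability scores.* With an assumed 95% of scores at zero, the simulated Wilcoxon error rate was 0.025; with 85% it was 0.047, and with 60% it was 0.050. At 0.025 the tolerability scales contribute 112 × 0.025 = 2.8 instead of 5.6, and the complete-null total becomes 5.6 + 2.8 = 8.4.
- *Unpaired t test.* The plan does not say that the t test is paired. On paired data with within-subject correlation 0.3 or 0.5 (assumed), an unpaired test had error rates of 0.0181 and 0.0054. The 3 × 16 = 48 lesion-count tests would then give 0.87 or 0.26 false positives, instead of 48 × 0.05 = 2.4.

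**7. What the count leaves out.** The subject questionnaire is also given at each visit, but its number of items is not stated. With an assumed 5, 10 or 20 ordinal items, the total is 304, 384 or 544 tests, and 15.2, 19.2 or 27.2 expected false positives under the complete null.

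**8. The other reading: one visit only.** With 14 tests, 14 × 0.05 = 0.7 false positives are expected. The chance of at least one is 1 − 0.95^14 = 51% if the tests are independent. If the visit is not named in advance, it can be chosen after the data are seen.

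**The case against.** The best defence is that the plan never says these measures are tested at every visit. It says only that change is judged at 0.05, and a row on a form shows data collection, not an analysis. This stands, so the count of 224 is conditional. It does not remove the point. The named tests compare two time points, no longitudinal model or summary measure is given, and if some other comparison is meant the readable plan does not say which.

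Second, the places where a visit or a status for these measures would most naturally appear are redacted. This also stands: a reader might infer that the plan contains no such rule anywhere, and the documents do not support that. What can be said is that the unredacted Section 12.2 and the readable synopsis paragraph set the rule without qualification.

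Third, a reader might infer that about 11 false findings are to be expected. That holds only if the product changes none of the 14 measures at any visit. The Introduction describes an approved acne drug with phase III efficacy, so unchanged lesion counts and IGA are unlikely. The null is more plausible for tolerability, since Section 11.1 calls irritation rare, but that is also where sparse scores lower the error rate.

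Fourth, the plan ranks its endpoints, and sharing a threshold with the primary does not make a lower tier confirmatory. That is fair, but the readable text attaches no descriptive label to the lower tiers and lets their changes be called significant.

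Finally, a formal correction such as Holm across all 14 measures would be a poor answer. Its first step requires p ≤ 0.05/14 = 0.0036, which makes real irritation harder to flag. It would also count total lesions alongside its two components. This stands and shapes the fix.

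**Conclusion.** The point holds in conditional form. The readable methods apply an unadjusted 0.05 rule to 14 non-sebum measures collected at 16 post-baseline visits, and give no visit for inference, testing order or descriptive label. If every visit is tested, there are 224 tests and up to about 11 false significant changes when nothing truly changes. The figure is about 5.6 if half of the nulls are true, and lower for sparse tolerability scores or an unpaired t test.

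The count rests on three assumptions: testing at every visit, which is inferred; test sizes close to 5%; and redacted text that does not already name visits or label these analyses. Unlisted questionnaire items would raise it. Because the plan states a positive rule for claiming significance, this is more than a missing detail. No multiplicity rule would separate product effect from natural course or regression to the mean in one arm.

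**What to change.** In the synopsis Statistical Methods and in Section 12:

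- Reserve the word significant for the primary sebum analysis.
- Report IGA, the three appearance scales and the three lesion counts at each visit as change from baseline with 95% confidence intervals, labelled descriptive and stated to be unadjusted.
- Report the seven tolerability scales as frequencies by visit, without multiplicity adjustment, so that irritation signals are not suppressed. This also suits the tolerability endpoint better than a signed rank test.

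If the redacted endpoint text already names visits or a descriptive status, a cross-reference from Section 12 would cover that part.

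The cost is a change of wording, with no new data, visits or subjects. The downside is that fewer supporting results can be called significant.
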